## 7. Initial Feasibility Analysis

Action report name:

For teriparatide vs. risedronate

Optum CDM - <https://bwh-dope.aetion.com/projects/details/1640/results/66361/result/0>

IBM® MarketScan®- <https://bwh-dope.aetion.com/projects/details/1641/results/66364/result/0>

Date conducted: 02/25/2021

Complete Action feasibility analysis using age and CCI as the only covariates and the primary endpoint (Section 6.3.1) as the outcome. No measures of association will be computed nor will incidence rates stratified by treatment group.

- Report patient characteristics by treatment group
- Report summary parameters of study population **FEASIBILITY- FOR STUDY OUTCOME**
- Report reasons for censoring in the overall study population
- Report overall risk of the primary outcome.

## 8. Initial Power Assessment

Action report name:

For teriparatide vs. risedronate

Optum CDM - <https://bwh-dope.aetion.com/projects/details/1640/results/66362/result/0>

IBM® MarketScan®- <https://bwh-dope.aetion.com/projects/details/1641/results/66363/result/0>

Date conducted: 02/25/2021

In order to complete the initial power analysis, the dummy outcome of a 90-day gap in database enrollment will be used. This outcome is used to ensure that no information on the comparative risks of the outcomes of interest are available at this stage. Complete a 1:1 PS-matched comparative analysis using this outcome. PS should include only 2 covariates: age and combined comorbidity index. Power calculations are based on the formulas from Chow et al. (2008).

- Stop analyses until feasibility and power are reviewed by primary investigators and FDA. Reviewers evaluate the results of the analyses described above in Sections 7 and 8, including numbers of patients, patient characteristics, follow-up time, and reasons for censoring by treatment group, as well as overall rates of outcomes and study power. These parameters are re-evaluated and reported in the subsequent sections, after incorporating feedback and refining the protocol.
- Stop analyses until feasibility and power are reviewed by primary investigators, FDA, and assigned members of advisory board.

|  |                                  |                |            |
|--|----------------------------------|----------------|------------|
| Reviewed by PI:                              | [name]
[name] | Date reviewed: | 03/17/2021 |
| Reviewed by FDA:                             | [name]                       | Date reviewed: | 03/16/2021 |
| Reasons for stopping analysis (if required): |                                  |                |            |

## 9. Balance Assessment

For teriparatide vs. risedronate

Optum CDM: <https://bwh-dope.action.com/projects/details/1640/rwrs/67726>

IBM® MarketScan®: <https://bwh-dope.action.com/projects/details/1641/rwrs/67727>

Date conducted: 03/29/21

After review of initial feasibility and power analyses, complete creation of the remaining covariates from Section 6.2. Again, using the dummy outcome of a 90-day gap in database enrollment, complete a 1:1 PS-matched analysis. The PS should include the complete list of covariates.

- Provide plot of PS distributions stratified by treatment group.

Note- Please refer to **Appendix B**.

- Report covariate balance after matching.

Note- For Table 1, please refer to **Appendix B**.

- Report reasons for censoring by treatment group.

|                                 | Overall | Referent | Exposure |
|---------------------------------|----------------|-----------------|-----------------|
| Dummy outcome                   | 0 (0%)         | 0 (0%)          | 0 (0%)          |
| Death                           | 28 (0.65%)     | 9 (0.21%)       | 19 (0.44%)      |
| End of patient enrollment       | 715 (16.5%)    | 300 (6.92%)     | 415 (9.58%)     |
| End of index exposure           | 157 (3.62%)    | 70 (1.62%)      | 87 (2.01%)      |
| Maximum follow-up time          | 442 (10.20%)   | 185 (4.27%)     | 257 (5.93%)     |
| End of index exposure           | 2775 (64.03%)  | 1522 (35.12%)   | 1253 (28.91%)   |
| Start of an additional exposure | 37 (0.85%)     | 9 (0.21%)       | 28 (0.65%)      |
| Nursing Home                    | 180 (4.15%)    | 72 (1.66%)      | 108 (2.49%)     |

- Report follow-up time by treatment group.

| Median Follow-Up Time (Days) [IQR] |                  |                         |
|---|------------------|-------------------------|
| Patient Group                      | Optum CDM | IBM® MarketScan® |
| Overall Patient Population                | 163.5 [88 - 415] | 190 [100 - 431.5]       |
| Referent - Risedronate                    | 148 [88 - 371]   | 148 [88 - 331]          |
| Exposure - Teriparatide                   | 192 [88 - 446]   | 234 [113 - 533]         |

- Report overall risk of the primary outcome.

|                         | Optum CDM | IBM® MarketScan® | Pooled |
|-------------------------|------------------|-------------------------|---------------|
| Risk per 1,000 patients | 15.9             | 18.9                    | 17.8          |

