| Excluded based on Exclusion criteria #15 - Oral bisphosphonate use                                  | -499 | 4886        | -1024 | 8499        |
| Excluded based on Exclusion criteria #16 - SERMs, Calcitonin, HRT                                   | -101 | 4785        | -321  | 8178        |
| Excluded based on Exclusion criteria #17 - Zoledronic acid use                                      | -2   | 4783        | -7    | 8171        |
| Excluded based on Exclusion criteria #18 - Intravenous ibandronate or pamidronate                   | -1   | 4782        | -1    | 8170        |
| Excluded based on Exclusion criteria #19 - Denosumab use  | -10  | 4772        | -4    | 8166        |
| Excluded based on Exclusion criteria #20 - PTH or PTH analogue use                                  | -44  | 4728        | -137  | 8029        |
| Excluded based on Exclusion criteria #21 - Romosozumab  | 0    | 4728        | 0     | 8029        |
| Final cohort  |      | 4728 |       | 8029 |

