### 6.2 Preliminary Covariates:

- Age
- Combined Comorbidity Index (CCI), measured over the baseline covariate assessment period, defined as 180 days prior to and

including index date.

Covariates listed above represent only a small subset of covariates that will ultimately be controlled for in the design and analysis. We use the covariates above only for initial feasibility analyses to judge whether there is likely to be sufficient overlap between treatment groups to proceed with the study. Remaining covariates are defined only after the study has passed the initial feasibility analysis and the initial power assessment and are listed in Table 1 (**Appendix B**). Gender is not included since the study is already restricted to female subjects.

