| 20   | History of excessive consumption of alcohol or abuse of drugs in the 1 year prior to Visit 2, in the opinion of the investigator.   | 
Measured 365 days prior to and including day of drug initiation in inpatient or outpatient care setting (any diagnosis position):
 
Alcohol Abuse or Dependence
ICD-9 diagnosis: 291.xx, 303.xx, 305.0x, 571.0x, 571.1x, 571.2x, 571.3x, 357.5x, 425.5x, E860.0x (CMS has not released mapping for new ICD10 for this code), V11.3x
ICD-10 diagnosis: F10.0x, K70.0x, G62.1, I42.6, 099.31x
 
OR
 
Drug Abuse or Dependence
ICD-9 diagnosis: 292.xx, 304.xx, 305.2x-305.9x, 648.3x
ICD-10 diagnosis: F11.x, F12.x, F13.x, F14.x, F15.x, F16.x, F17.2x, F18.x, F19.x, F55.2, G62.0, 099.32x
 
OR
 
Non-compliance
ICD-9 diagnosis: V45.12, V15.81
ICD-10 diagnosis: Z91.19, Z91.15
 | 
Paterno, Elisabetta et al. "Cardiovascular outcomes associated with canagliflozin versus other non-gliflozin antidiabetic drugs: population based cohort study." BMJ 2018;360:k119
http://dx.doi.org/10.1136/bmj.k119
 
Paterno, Elisabetta et al. "Empagliflozin and the Risk of Heart Failure Hospitalization in Routine Clinical Care: A First Analysis from the Empagliflozin Comparative Effectiveness and Safety (EMPRISE) Study." Circulation 2019 Apr 8. doi: 10.1161/CIRCULATIONAHA.118.039177
 |
| 21.1 | Previous treatment with the following bone active drugs is allowed but treatment must be discontinued at Visit 1 or at the time indicated below:
1. Oral bisphosphonates (including alendronate, risedronate, ibandronate, etidronate).  | 
Measured 180 days prior to and 1 day before the day of drug initiation:
 
Generic names:
Alendronate, Ibandronate, Risedronate, Etidronate, Tiludronate
   |  |
| 21.2 | 2. SERMs, calcitonin, estrogen (oral, transdermal, or injectable), progestin, estrogen analog, estrogen agonist, estrogen antagonist or tibolone, androgens, strontium ranelate, or active vitamin D3 analogues.  | 
Measured 30 days prior to and 1 day before the day of drug initiation:
 
Generic names:
SERMs: OSPEMIFENE, RALOXIFENE HCL, ESTROGENS, CONJUGATED/BAZEDOXIFENE ACETATE
Calcitonin
HRT: estrogens, progestins, androgens
  | 
Strontium not approved in USA for treatment of osteoporosis.
 
Vitamin D3 analogues over the counter
   |

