## Appendix B

|   |                      |                      |        |                     |                     |        |               |               |        |
|---|----------------------|----------------------|--------|---------------------|---------------------|--------|---------------|---------------|--------|
| Digoxin; n (%)  | 18 (2.4%)            | 14 (1.9%)            | 0.034  | 45 (3.2%)           | 38 (2.7%)           | 0.030  | 063 (2.9%)    | 052 (2.4%)    | 0.031  |
| Use of Diuretics; n (%)*  | 205 (27.4%)          | 220 (29.5%)          | -0.047 | 466 (32.8%)         | 466 (32.8%)         | 0.000  | 671 (31.0%)   | 686 (31.7%)   | -0.015 |
| Use of Aspirin; n (%)   | 5 (0.7%)             | 5 (0.7%)             | 0.000  | 25 (1.8%)           | 24 (1.7%)           | 0.008  | 030 (1.4%)    | 029 (1.3%)    | 0.009  |
| NSAIDs (NOT including aspirin); n (%)                                   | 203 (27.2%)          | 188 (25.2%)          | 0.045  | 377 (26.5%)         | 318 (22.4%)         | 0.096  | 580 (26.8%)   | 506 (23.4%)   | 0.078  |
| HRT (Use of estrogens, progestins, androgens); n (%)*                   | 47 (6.3%)            | 44 (5.9%)            | 0.017  | 84 (5.9%)           | 93 (6.5%)           | -0.025 | 131 (6.0%)    | 137 (6.3%)    | -0.012 |
| Other Pressors; n (%)   | 5 (0.7%)             | 5 (0.7%)             | 0.000  | 8 (0.6%)            | 20 (1.4%)           | -0.080 | 013 (0.6%)    | 025 (1.2%)    | -0.064 |
| Use of Statins; n (%)*  | 258 (34.5%)          | 252 (33.7%)          | 0.017  | 521 (36.7%)         | 523 (36.8%)         | -0.002 | 779 (35.9%)   | 775 (35.8%)   | 0.002  |
| Selective Estrogen Receptor Modulators (SERMs); n (%)*                  | 7 (0.9%)             | 19 (2.5%)            | -0.124 | 31 (2.2%)           | 38 (2.7%)           | -0.032 | 038 (1.8%)    | 057 (2.6%)    | -0.055 |
| Healthcare Utilization Measures                                  |                      |                      |        |                     |                     |        |               |               |        |
| Use of any drugs claims*  |                      |                      |        |                     |                     |        |               |               |        |
| ...mean (sd)  | 24.76 (18.01)        | 24.95 (18.56)        | -0.010 | 25.89 (19.03)       | 25.43 (18.22)       | 0.025  | 25.50 (18.68) | 25.26 (18.34) | 0.013  |

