| ...Missing; n (%)   | NA                   | NA                   | NA     | NA                  | NA                  | NA     | NA            | NA            | NA     |
| Business Type*   |                      |                      |        |                     |                     |        |               |               |        |
| ...Commercial; n (%)  | 291 (39.0%)          | 291 (39.0%)          | 0.000  | NA                  | NA                  | NA     | 291 (39.0%)   | 291 (39.0%)   | 0.000  |
| ...Medicare; n (%)  | 456 (61.0%)          | 456 (61.0%)          | 0.000  | NA                  | NA                  | NA     | 456 (61.0%)   | 456 (61.0%)   | 0.000  |
| Insurance Plan Type*   |                      |                      |        |                     |                     |        |               |               |        |
| ...Comprehensive; n (%)   | NA                   | NA                   | NA     | 413 (29.1%)         | 431 (30.4%)         | -0.028 | 413 (29.1%)   | 431 (30.4%)   | -0.028 |
| ...HMO; n (%)   | NA                   | NA                   | NA     | 97 (6.8%)           | 104 (7.3%)          | -0.020 | 97 (6.8%)     | 104 (7.3%)    | -0.020 |
| ...PPO; n (%)   | NA                   | NA                   | NA     | 731 (51.5%)         | 705 (49.6%)         | 0.038  | 731 (51.5%)   | 705 (49.6%)   | 0.038  |
| ...Others; n (%)  | NA                   | NA                   | NA     | 179 (12.6%)         | 180 (12.7%)         | -0.003 | 179 (12.6%)   | 180 (12.7%)   | -0.003 |

\*Included in the 1:1 PS matching model

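### The MarketScan hospitalization row in Appendix B repeats hospital days, and the propensity score has no vertebral-fracture timing or number and no earlier use of four bone-drug classes

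*Combined protocol and SAP*

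**What the plan says.** Section 6.2 names only age and the combined comorbidity index. It adds that "Remaining covariates are defined only after the study has passed the initial feasibility analysis" and the initial power assessment, and refers to Table 1 in Appendix B for them. Section 9 then tells the analyst to "complete creation of the remaining covariates from Section 6.2", and says "The PS should include the complete list of covariates". In the matched table an asterisk means "Included in the 1:1 PS matching model".

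The starred fracture rows are hip/femur fractures and other fractures. The starred bone-drug rows are "HRT (Use of estrogens, progestins, androgens); n" and "Selective Estrogen Receptor Modulators (SERMs); n". Vertebral fracture appears only as an entry rule in Appendix A: a qualifying code at any time from enrollment to 90 days before initiation, and none after that. Earlier bone drugs appear only as exclusions (Appendix A, 21.1 to 21.5): 180 days for oral bisphosphonates and denosumab, 365 for zoledronic acid, 30 for calcitonin. The flowchart in Section 5.3 handles calcitonin together with SERMs and HRT ("Excluded based on Exclusion criteria #16 - SERMs, Calcitonin, HRT"), and Appendix A gives the three one window ("Measured 30 days prior to and 1 day before the day of drug initiation").

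Appendix B also has starred rows for number of hospitalizations and number of hospital days.

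**The concern.** The outcome is a further vertebral fracture in women who have all had one. How many they had, how recently, and which bone drugs they took earlier could affect both the choice of teriparatide and the risk of the next fracture. VERO also allowed earlier bone drugs, but randomization balanced them; here only the propensity score can. The plan is uneven: SERM and HRT use outside the 30-day window is matched on, while calcitonin, which has the same window, has no row.

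The hospitalization row is a different problem: a visible error in a table that was reviewed before the study could proceed (Section 10, 04/15 and 04/16/2021). If only the table is wrong, MarketScan balance on admission count is unverified. If the input is wrong, the MarketScan score used one quantity twice and admissions not at all.

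**Working it through.** **1. The repeated row (Appendix B, MarketScan, mean (SD)).**

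| | Risedronate | Teriparatide | Std. diff. |
|---|---|---|---|
| Hospitalizations, unmatched | 1.83 (6.41) | 2.30 (5.88) | -0.076 |
| Hospital days, unmatched | 1.83 (6.41) | 2.30 (5.88) | -0.076 |
| Hospitalizations, matched | 2.09 (5.83) | 2.09 (5.52) | 0.000 |
| Hospital days, matched | 2.09 (5.83) | 2.09 (5.52) | 0.000 |

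In Optum the rows differ (matched risedronate: 0.46 stays, 5.18 days).

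The pooled means reproduce from the repeated values. Unmatched arm sizes come from summing the age categories (Optum 3,875 and 853; MarketScan 6,464 and 1,565).
- Unmatched risedronate: (3,875×0.32 + 6,464×1.83)/10,339 = 1.26
- Unmatched teriparatide: (853×0.48 + 1,565×2.30)/2,418 = 1.66
- Matched, each arm: (747×0.46 + 1,420×2.09)/2,167 = 1.53

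Plausibility: divide the mean by the share hospitalized (older plus recent flags, the largest possible share).
- MarketScan matched risedronate: 2.09/(384/1,420) = 7.7 stays per hospitalized patient
- Optum matched risedronate: 0.46/(177/747) = 1.9

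Across arms, before and after matching, and using the older flag alone or both flags, the ranges are 7.6–9.1 in MarketScan and 1.8–2.1 in Optum. This assumes that the count covers about the same period as the flags (day -450 onward); its window is not stated. So the figure looks like days. That is an inference: read as days it gives 7.6–7.7 per hospitalized matched patient, against 20.0–21.9 in Optum. If MarketScan had Optum's stays per patient (assumption), its matched mean would be about 0.46–0.59 and the pooled mean about 0.46–0.54.

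**2. The missing history.** I read every row of both tables. None gives vertebral-fracture number or time since fracture, and none gives oral bisphosphonate, zoledronic acid, denosumab or calcitonin use. The nearest recorded measures, pooled:
- Hip/femur fractures: before matching, (207/2,418)/(442/10,339) = 8.6%/4.3% = 2.0; after, 147/146 = 1.01
- Other fractures: before, (322/2,418)/(692/10,339) = 13.3%/6.7% = 2.0; after, 255/260 = 0.98

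Other fractures cover about 12% of a matched cohort in which every patient has a vertebral-fracture code, so that row cannot stand in for vertebral-fracture history.

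**3. How much bias would matter.** Power = Φ(|ln HR|·√(D/4) − 1.96). At HR 0.44:
- Pooled, D = 77.1452: 0.950 (plan 0.950)
- Optum, D = 23.7546: 0.516 (plan 0.516)
- MarketScan, D = 53.676: 0.853 (plan 0.853)

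Solving the pooled formula for HR:
- Power 0.90 at HR 0.478, a shift of 0.478/0.44 = 1.09
- Power 0.80 at HR 0.528, a shift of 1.20
- The trial's upper confidence limit, 0.68, needs a shift of 0.68/0.44 = 1.55

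These cover only bias that raises the HR. In the other direction, a factor of 0.44/0.68 = 0.65 would make a true HR of 0.68 look like the trial's 0.44, with no loss of apparent power.

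**4. Complete list against starred list.** Set aside sub-rows of starred composites, and continuous age (its categories are starred). Then 16 stand-alone rows have no asterisk, or 17 if CABG/PTCA is counted separately. They include the combined comorbidity score, which Section 6.2 names, and the frailty score. All are below 0.10 in both databases after matching; the largest is NSAIDs, MarketScan, 0.096.

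**The case against.** Much of the risk is already handled. Fractures in the last 90 days and recent bone drugs are excluded by design, and allowing earlier use follows VERO. Markers of severity and specialist care balance well after matching: both fracture rows, falls, opioids, corticosteroids, DXA tests and endocrinologist visits. The last two were clearly imbalanced in Optum before matching (-0.301 and -0.372) and are 0.000 and -0.017 after. On this view, further covariates are a matter of judgement. That stands as far as size goes. It does not remove the gap, because balance on proxies does not establish balance on a variable nobody tabulated.

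The hospitalization row may be only a copying slip. Other printed cells are wrong: MarketScan entry from 2016 on, 8.3% vs 18.0%, is printed as -0.027 but computes to about -0.29; Optum blood chemistry, 67.4% vs 77.4%, is printed as -0.012 but computes to about -0.22. Hospital days and both hospitalization flags are balanced. This makes a table error credible, but does not settle whether the score was affected.

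A reader might infer that teriparatide patients remain sicker after matching and that the HR is biased upward. The twofold excess of other recorded fractures before matching makes an imbalance in vertebral history plausible, but those rows balance afterwards and vertebral history itself is not reported. For earlier drug use even the direction is unknown. The Optum SERM row (7 vs 19 patients, -0.124) is sparse and says nothing about other drugs.

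**Conclusion.** One table row is wrong and must be corrected: MarketScan number of hospitalizations, and the pooled row built from it. It would go too far to say that the propensity score used hospital days twice, or that the balance review is void; the fitted model has to be checked.

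The missing vertebral-fracture and drug history is a real gap in confounding control, and closing it is a cheap safeguard rather than the correction of a demonstrated bias. Its effect cannot be computed, because the documents give no such history by arm. The break-even factors of 1.09 and 1.20 rest on the plan's 77.1 events and HR of 0.44, and do not bound bias in the other direction. The mismatch between Section 9 and the asterisks is minor.

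**What to change.** Section 13 is still undated and blank, so all of this can be done before any outcome comparison.

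(a) Rebuild the MarketScan hospitalization count, correct the pooled row, and state whether the score used days twice. If it did, re-matching is required whatever is decided on (b) and (c).

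(b) Add to Table 1 and the score an indicator for each osteoporosis drug class used before its exclusion window, within the 365-day baseline (for example, days -365 to -181 for oral bisphosphonates and denosumab, -365 to -31 for calcitonin). Zoledronic acid's window fills the baseline, so cover it in an all-available-history version run as a sensitivity analysis.

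(c) Add one vertebral-fracture history variable for days -365 to -90: none recorded; one, by recency band; two or more. A separate count and recency variable would overlap, since a count of zero and nothing recorded within the year are the same patients. State a 90-day gap rule for separate fractures. Use the study's full code list, and first reconcile S32.x, which is in the Appendix A entry codes but not in the outcome string as printed; that string is visibly damaged and the full list is held outside the document.

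(d) Make Section 9 and the starred list agree, stating which rows are balance checks only.

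(e) Re-run matching, balance and power, re-check the Optum SERM row, and report the pairs lost.

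The programming cost is small. The statistical cost is some misclassified fracture counts (close fractures merged, older ones ignored), unequal lookback in the all-history version, and an unknown loss of pairs. Matching has already dropped 853 − 747 = 106 Optum and 1,565 − 1,420 = 145 MarketScan teriparatide patients. If a further 5%, 10% or 20% of pairs were lost (assumption, same risk and HR), pooled power would be 0.940, 0.928 or 0.897, and Optum power 0.496, 0.475 or 0.432.

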| Use of Benzodiazepine; n (%)  | 568 (14.7%)       | 200 (23.4%)       | -0.223 | 1,491 (23.1%)     | 433 (27.7%)       | -0.106 | 2,059 (19.9%) | 633 (26.2%)   | -0.150 |
| All antidiabetic medications; n (%)   | 439 (11.3%)       | 82 (9.6%)         | 0.056  | 670 (10.4%)       | 188 (12.0%)       | -0.051 | 1,109 (10.7%) | 270 (11.2%)   | -0.016 |
| ACE/ARB; n (%)  | 1,555 (40.1%)     | 280 (32.8%)       | 0.152  | 2,234 (34.6%)     | 527 (33.7%)       | 0.019  | 3,789 (36.6%) | 807 (33.4%)   | 0.067  |
| Use of Anticoagulants; n (%)  | 301 (7.8%)        | 81 (9.5%)         | -0.061 | 548 (8.5%)        | 176 (11.2%)       | -0.091 | 849 (8.2%)    | 257 (10.6%)   | -0.082 |
| Use of Amiodarone; n (%)  | 36 (0.9%)         | 10 (1.2%)         | -0.029 | 81 (1.3%)         | 26 (1.7%)         | -0.033 | 117 (1.1%)    | 036 (1.5%)    | -0.035 |
| Digoxin; n (%)  | 92 (2.4%)         | 17 (2.0%)         | 0.027  | 233 (3.6%)        | 45 (2.9%)         | 0.039  | 325 (3.1%)    | 062 (2.6%)    | 0.030  |
| Use of Diuretics; n (%)   | 1,273 (32.9%)     | 251 (29.4%)       | 0.076  | 2,096 (32.4%)     | 515 (32.9%)       | 0.011  | 3,369 (32.6%) | 766 (31.7%)   | 0.019  |
| Use of Aspirin; n (%)   | 24 (0.6%)         | 6 (0.7%)          | -0.012 | 90 (1.4%)         | 25 (1.6%)         | -0.016 | 114 (1.1%)    | 031 (1.3%)    | -0.018 |
| NSAIDs (NOT including aspirin); n (%)   | 807 (20.8%)       | 218 (25.6%)       | -0.114 | 1,496 (23.1%)     | 365 (23.3%)       | -0.005 | 2,303 (22.3%) | 583 (24.1%)   | -0.043 |
| HRT (Use of estrogens, progestins, androgens); n (%)  | 240 (6.2%)        | 50 (5.9%)         | 0.013  | 445 (6.9%)        | 102 (6.5%)        | 0.016  | 685 (6.6%)    | 152 (6.3%)    | 0.012  |
| Other Pressors; n (%)   | 24 (0.6%)         | 5 (0.6%)          | 0.000  | 38 (0.6%)         | 24 (1.5%)         | -0.088 | 062 (0.6%)    | 029 (1.2%)    | -0.064 |
| Use of Statins; n (%)   | 1,599 (41.3%)     | 276 (32.4%)       | 0.185  | 2,393 (37.0%)     | 568 (36.3%)       | 0.015  | 3,992 (38.6%) | 844 (34.9%)   | 0.077  |
| Selective Estrogen Receptor Modulators (SERMs); n (%)   | 61 (1.6%)         | 19 (2.2%)         | -0.044 | 128 (2.0%)        | 39 (2.5%)         | -0.034 | 189 (1.8%)    | 058 (2.4%)    | -0.042 |

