| Premature menopause; n (%)   | 1 (0.1%)          | 3 (0.4%)          | -0.060 | 1 (0.1%)          | 1 (0.1%)          | 0.000  | 002 (0.1%)    | 004 (0.2%)    | -0.026 |
| Oophorectomy; n (%)  | 1 (0.1%)          | 0 (0.0%)          | 0.045  | 0 (0.0%)          | 1 (0.1%)          | -0.045 | 001 (0.0%)    | 001 (0.0%)    | 0.000  |
| COPD; n (%)*   | 123 (16.5%)       | 130 (17.4%)       | -0.024 | 214 (15.1%)       | 207 (14.6%)       | 0.014  | 337 (15.6%)   | 337 (15.6%)   | 0.000  |
| Asthma; n (%)*   | 80 (10.7%)        | 88 (11.8%)        | -0.035 | 132 (9.3%)        | 135 (9.5%)        | -0.007 | 212 (9.8%)    | 223 (10.3%)   | -0.017 |
| Obstructive sleep apnea; n (%)*  | 49 (6.6%)         | 48 (6.4%)         | 0.008  | 56 (3.9%)         | 50 (3.5%)         | 0.021  | 105 (4.8%)    | 098 (4.5%)    | 0.014  |
| Syncope; n (%)*  | 39 (5.2%)         | 45 (6.0%)         | -0.035 | 77 (5.4%)         | 85 (6.0%)         | -0.026 | 116 (5.4%)    | 130 (6.0%)    | -0.026 |
| Falls; n (%)*  | 134 (17.9%)       | 142 (19.0%)       | -0.028 | 79 (5.6%)         | 81 (5.7%)         | -0.004 | 213 (9.8%)    | 223 (10.3%)   | -0.017 |
| VTE; n (%)   | 33 (4.4%)         | 32 (4.3%)         | 0.005  | 49 (3.5%)         | 47 (3.3%)         | 0.011  | 082 (3.8%)    | 079 (3.6%)    | 0.011  |
| Gait abnormality; n (%)*   | 141 (18.9%)       | 140 (18.7%)       | 0.005  | 167 (11.8%)       | 166 (11.7%)       | 0.003  | 308 (14.2%)   | 306 (14.1%)   | 0.003  |
| Osteopenia; n (%)*   | 256 (34.3%)       | 247 (33.1%)       | 0.025  | 316 (22.3%)       | 315 (22.2%)       | 0.002  | 572 (26.4%)   | 562 (25.9%)   | 0.011  |
| History of hip and femur fractures; n (%)*   | 41 (5.5%)         | 45 (6.0%)         | -0.021 | 105 (7.4%)        | 102 (7.2%)        | 0.008  | 146 (6.7%)    | 147 (6.8%)    | -0.004 |
| Other Fractures; n (%)*  | 90 (12.0%)        | 95 (12.7%)        | -0.021 | 170 (12.0%)       | 160 (11.3%)       | 0.022  | 260 (12.0%)   | 255 (11.8%)   | 0.006  |
| Glucocorticoid-Induced Osteoporosis; n (%)*  | 2 (0.3%)          | 2 (0.3%)          | 0.000  | 1 (0.1%)          | 2 (0.1%)          | 0.000  | 003 (0.1%)    | 004 (0.2%)    | -0.026 |
| Combined comorbidity score  |                   |                   |        |                   |                   |        |               |               |        |

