| ...mean (sd)   | 1.20 (2.17)       | 1.25 (2.25)       | -0.023 | 0.90 (1.71)       | 0.86 (1.72)       | 0.023  | 1.00 (1.88)   | 0.99 (1.92)   | 0.005  |
| ...median [IQR]  | 1.00 [0.00, 2.00] | 1.00 [0.00, 2.00] | 0.000  | 0.00 [0.00, 2.00] | 0.00 [0.00, 1.00] | 0.000  | 0.34 (1.88)   | 0.34 (1.92)   | 0.000  |
| Frailty Score: Empirical Version 365 days as Categories   |                   |                   |        |                   |                   |        |               |               |        |
| ...<0.12908; n (%)   | 317 (42.4%)       | 318 (42.6%)       | -0.004 | 476 (33.5%)       | 472 (33.2%)       | 0.006  | 793 (36.6%)   | 790 (36.5%)   | 0.002  |
| ...0.12908 - 0.1631167; n (%)  | 158 (21.2%)       | 155 (20.7%)       | 0.012  | 309 (21.8%)       | 318 (22.4%)       | -0.014 | 467 (21.6%)   | 473 (21.8%)   | -0.005 |
| ...>= 0.1631167; n (%)   | 272 (36.4%)       | 274 (36.7%)       | -0.006 | 635 (44.7%)       | 630 (44.4%)       | 0.006  | 907 (41.9%)   | 904 (41.7%)   | 0.004  |
| Medication Use  |                   |                   |        |                   |                   |        |               |               |        |
| Use of oral corticosteroids; n (%)*  | 268 (35.9%)       | 266 (35.6%)       | 0.006  | 498 (35.1%)       | 506 (35.6%)       | -0.010 | 766 (35.3%)   | 772 (35.6%)   | -0.006 |
| Use of antidepressants; n (%)*   | 256 (34.3%)       | 275 (36.8%)       | -0.052 | 606 (42.7%)       | 576 (40.6%)       | 0.043  | 862 (39.8%)   | 851 (39.3%)   | 0.010  |
| Use of anticonvulsants; n (%)*   | 159 (21.3%)       | 149 (19.9%)       | 0.035  | 323 (22.7%)       | 311 (21.9%)       | 0.019  | 482 (22.2%)   | 460 (21.2%)   | 0.024  |
| Use of beta blocker OR calcium channel blocker; n (%)*   | 250 (33.5%)       | 235 (31.5%)       | 0.043  | 471 (33.2%)       | 478 (33.7%)       | -0.011 | 721 (33.3%)   | 713 (32.9%)   | 0.009  |
| Use of PPIs; n (%)*  | 222 (29.7%)       | 219 (29.3%)       | 0.009  | 488 (34.4%)       | 501 (35.3%)       | -0.019 | 710 (32.8%)   | 720 (33.2%)   | -0.009 |
| Use of opioids; n (%)*   | 419 (56.1%)       | 420 (56.2%)       | -0.002 | 848 (59.7%)       | 853 (60.1%)       | -0.008 | 1,267 (58.5%) | 1,273 (58.7%) | -0.004 |
| Use of antipsychotics; n (%)*  | 21 (2.8%)         | 24 (3.2%)         | -0.023 | 53 (3.7%)         | 54 (3.8%)         | -0.005 | 074 (3.4%)    | 078 (3.6%)    | -0.011 |

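### Section 9 calls for a propensity score with the complete covariate list, but the fitted model in Appendix B omits about 14 to 17 listed covariates, including CCI, frailty and NSAID use, without a reason

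*Combined protocol and SAP*

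**What the plan says.** Section 6.2 names age and CCI as preliminary covariates and adds: "Covariates listed above represent only a small subset of covariates that will ultimately be controlled for in the design and analysis". It sends the reader to Table 1 in Appendix B for the rest. Section 8 uses a PS with age and CCI only, for the first power assessment. Section 9 then moves to the full model: "The PS should include the complete list of covariates".

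In the PS-matched table of Appendix B, an asterisk on a row means "Included in the 1:1 PS matching model". The rows "Combined comorbidity score", "Frailty Score: Empirical Version 365 days as Categories" and "NSAIDs (NOT including aspirin); n" (%) carry no asterisk, and neither do a number of others. Neither Section 6.2, Section 9 nor Appendix B says why. Section 13, which would hold the comparative analyses, is empty, so no outcome-model adjustment is specified that could pick up what the PS leaves out.

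**The concern.** The matched cohort was not built by the rule the plan states. That cohort determines the balance table, the 2,167 pairs and the power in Section 10, and every later comparison. A reader cannot tell whether covariates were left out for a reason fixed in advance or after balance had been inspected. CCI is the clearest case: it is one of only two covariates in the Section 8 model and is then absent from the full one.

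A covariate outside the PS is balanced only as far as its correlates inside the PS balance it. For NSAID use that was not enough in MarketScan or in the pooled data, where the arms are further apart after matching than before.

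**Working it through.** **1. Which rows are outside the model.** In the matched table, 36 covariate rows have no asterisk. Continuous age is not counted, because age categories are in the model.

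- 19 are components of a starred composite: obesity, overweight, five coronary rows, stroke, TIA, late effects, atrial fibrillation, other dysrhythmia, three diabetes rows, eating disorders, enteritis/colitis, postprocedural digestive disorders, and gout.
- 1 is CABG/PTCA, which the label of the starred coronary composite does not mention.
- 16 remain: Parkinson's disease, seizure disorders, delirium/psychosis, CKD IV-V/ESRD, premature menopause, oophorectomy, VTE, CCI, frailty score, amiodarone, digoxin, aspirin, NSAIDs, other pressors, recent hospitalization, old hospitalizations.

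The count is 16 with CABG/PTCA placed under coronary disease and 17 with it standing alone. It falls to 14 or 15 if the two hospitalization rows are treated as parts of the starred number of hospitalizations. No convention brings in CCI, frailty or NSAIDs.

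**2. Is there a visible rule?** Rarity does not explain the omissions. Glucocorticoid-induced osteoporosis is starred with 3 + 4 = 7 matched patients, while NSAIDs are unstarred with 580 + 506 = 1,086. Redundancy does not explain them either. Other rheumatic disorders is starred alongside its own starred composite, while NSAIDs, VTE and delirium/psychosis belong to no composite.

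**3. NSAID balance.** The standardized difference is (pR - pT) / sqrt{[pR(1 - pR) + pT(1 - pT)] / 2}, with R for risedronate and T for teriparatide. The unmatched group sizes come from summing the age categories: Optum 3,875 and 853, MarketScan 6,464 and 1,565, pooled 10,339 and 2,418. The matched sizes per arm are 747, 1,420 and 2,167.

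MarketScan after matching: pR = 377/1,420 = 0.2655 and pT = 318/1,420 = 0.2239. The difference is 0.0415 and the denominator 0.4294, which gives 0.097. The table states 0.096, which is what the formula gives from the rounded percentages 26.5% and 22.4%.

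| | Before: stated (from counts) | After: stated (from counts) | Change |
|---|---|---|---|
| MarketScan | -0.005 (-0.004) | 0.096 (0.097) | worse |
| Pooled | -0.043 (-0.044) | 0.078 (0.079) | worse, sign reversed |
| Optum | -0.114 (-0.112) | 0.045 (0.046) | better |

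The plan's figures are reproduced to within rounding of the percentages. A two-proportion test on the matched counts gives z = 2.58 in MarketScan (p = 0.010), 2.59 pooled (p = 0.0095) and 0.88 in Optum.

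**4. Other omitted rows, stated standardized differences.**

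- Delirium/psychosis, MarketScan: -0.054 before, -0.085 after (35 vs 57 patients).
- CCI, pooled: -0.134 before, 0.005 after.
- Frailty: at most 0.014 in absolute value after matching, in any category and either database.
- Old hospitalizations, pooled: -0.180 before, -0.007 after.
- Mean age (bands only in the model): -0.016 Optum, -0.022 MarketScan, -0.020 pooled after matching.

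No omitted stand-alone covariate reaches 0.10 after matching in either database or pooled.

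**5. Possible size.** The documents give no fracture rate by NSAID use. As an assumption only, let NSAID users have 1.5 to 2.0 times the outcome rate (RR). The NSAID imbalance taken alone would multiply the pooled hazard ratio by [1 + pT(RR - 1)] / [1 + pR(RR - 1)], with pT = 506/2,167 = 0.2335 and pR = 580/2,167 = 0.2677:

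- RR 1.5: 1.1168/1.1338 = 0.985, a log shift of 0.015.
- RR 2.0: 1.2335/1.2677 = 0.973, a log shift of 0.027.

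With the 77.1 events expected in Section 10, the standard error of the log hazard ratio is about 2/sqrt(77.1) = 0.23. The shift is 7% to 12% of one standard error.

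**The case against.** The strongest reply is that this is a documentation gap. In context, the complete list is set against the two-covariate model of Section 8. The fitted model is disclosed row by row, and the investigators' and FDA review dates follow it with no stopping reason entered. Nobody would want every row in the model: components of a composite are redundant, and in Optum oophorectomy is 5 vs 0 before matching, which would cause separation. Several omitted rows are very rare after matching (oophorectomy 2, Parkinson's disease 5, premature menopause 6).

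Inclusion in the model does not guarantee balance either. SERM use in Optum is starred and went from -0.044 to -0.124 (7 vs 19). P values are a poor measure of balance, and with this many rows some small ones are expected by chance.

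Most of this stands, and it limits the size of the point. It does not remove the contradiction. Disclosing the reduced model does not justify it, and sparsity cannot account for NSAIDs, CCI, frailty or old hospitalizations.

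Two stronger readings are tempting, and the documents support neither.

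- A reader might infer a bias in favor of teriparatide from the excess of NSAID users on risedronate. No net direction is shown. Delirium/psychosis and other pressors (8 vs 20 in MarketScan) are more frequent on teriparatide. Opioid use (-0.004 pooled) and osteoarthritis (-0.025) are in the model and balanced, so pain is partly covered.
- A reader might infer that the age-tertile subgroups are unbalanced because age enters only in bands. No within-band ages are reported, the tertile cut-points are blank in Section 6.3.2, and mean age is balanced.

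**Conclusion.** The point holds as a departure from the plan's own rule with a modest visible consequence. The instruction and the reported model disagree on about 14 to 17 stand-alone covariates, and no reason is given. NSAID balance worsened in MarketScan and pooled and improved in Optum; delirium/psychosis worsened in MarketScan. CCI, frailty and mean age are balanced although CCI, frailty and continuous age are not in the model. The 0.10 benchmark used here is conventional; the plan sets no threshold.

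The effect on the hazard ratio is likely to be small. The calculation above rests on an assumed rate ratio and takes one covariate in isolation, so it gives an order of magnitude and not an estimate of bias. The point also rests on the asterisks being a complete record of the fitted model, which is how the footnote reads.

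**What to change.** The comparative-analysis date in Section 13 is blank, so on the documents the change can still precede any outcome comparison.

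1. Refit the PS in each database with the omitted stand-alone covariates that are frequent enough to estimate: at least CCI, the frailty score, NSAIDs, delirium/psychosis, VTE, CKD IV-V and the hospitalization indicators.
2. In Sections 6.2 and 9, name each row left out for sparsity (such as oophorectomy, premature menopause and Parkinson's disease) and give the reason. State that components of an included composite are not entered separately.
3. Rematch, then restate the balance in Appendix B and the matched N and power in Section 10.

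The cost is one rerun of the PS and matching in two databases, a repeat of the review that Section 10 requires, and possibly a few fewer pairs with slightly lower stated power. The covariates are already built, so no new data work is needed.
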